2.4 Study Rationale and Benefit-Risk Assessment

Class I phosphatidylinositol 3-kinase (PI3K) is a lipid kinase with a catalytic subunit that exists in 4 different isoforms: α , β , δ , and γ . Activation of PI3K generates lipid second messengers at the cell membrane that recruit and activate multiple intracellular enzymes that are regulators of cell proliferation, survival, and motility. The α and β isoforms are widely expressed in many tissues, and the phosphatidylinositol 3-kinase γ isoform (PI3K γ) has a particular role in T-cell activation, PI3K δ expression is largely restricted to hematopoietic cells (Brown 2014). In B-lymphocytes, the δ isoform (PI3K δ) plays a central role in normal B-cell development and function, transducing signals from the B-cell receptor as well as from receptors for various cytokines, chemokines, and integrins (Durand 2009, Bilancio 2006). PI3K δ signaling pathways are commonly hyperactive in B-cell malignancies, making inhibition of PI3K δ a promising target in the therapy of B-cell NHL (Lanutti 2011, Hoellenriegel 2011).

PI3K δ inhibitors have proven activity in relapsed/refractory lymphoma setting, with four agents receiving accelerated approval from the United States Food and Drug Administration (FDA) for the treatment of follicular lymphoma, (idelalisib, copanlisib, duvelisib and umbralisib). Additionally, umbralisib is also approved in the United States for the treatment of MZL.

In the idelalisib phase 2 study in patients with relapsed iNHL, 125 patients, including 72 FL, 28 SLL, 15 MZL, and 10 lymphoplasmacytic lymphoma/Waldenström's macroglobulinemia

(LPL/WM), were enrolled and treated with idelalisib as a single agent (Gopal 2014). The ORR was 57% (71/125 patients), with 6% meeting the criteria for a CR. The median time to a response (TTR) was 1.9 months, the median DoR was 12.5 months, and the median progression-free survival (PFS) was 11 months. Similar response rates were observed across all subtypes. The most common adverse events of grade 3 or higher were neutropenia (27%), elevations in transaminase levels (13%), diarrhea (13%), and pneumonia (7%). For the patients with relapsed/refractory MCL enrolled in phase 1 study, idelalisib also showed tolerable toxicity and anti-tumor activities: patients without DLT and no evidence of disease progression after 48 weeks enrolled in the extension study (Kahl 2014). Common Grade ≥ 3 AEs included diarrhea (45%), decreased appetite (75%), transaminase levels elevations (33%). ORR was 40% (16/40 patients), with CR 5% (2/40). Median DoR was 2.7 months, median PFS was 3.7 months, and 1-year PFS was 22%. Based on this study, FDA approved idelalisib for the treatment of patients with relapsed FL or SLL who have received at least two prior systemic therapies.

In the phase 3 study among patients with relapsed CLL who were less able to undergo chemotherapy, the combination of idelalisib and rituximab, as compared with placebo and rituximab, significantly improved progression-free survival (mean PFS: not reached in the idelalisib group and 5.5 months in the placebo group [hazard ratio for progression or death in the idelalisib group = 0.15; $P < 0.001$]), ORR (81% vs. 13%; odds ratio, 29.92; $P < 0.001$), and overall survival (OS) at 12 months (92% vs. 80%; hazard ratio for death, 0.28; $P = 0.02$). Serious adverse events occurred in 40% of the patients receiving idelalisib and rituximab and in 35% of those receiving placebo and rituximab. Based on the study results, FDA approved idelalisib for the treatment of patients with relapsed CLL, in combination with rituximab (Furman 2014).

In a single-arm, multicenter, phase 2 clinical trial to evaluate the efficacy of copanlisib (PI3K α/δ inhibitor) in relapse NHL, a total of 142 patients were enrolled, including 104 FL patients, who have received at least two prior treatments, including rituximab and an alkylating agent (Dreyling 2017). The ORR in FL patients was 59%, with 14% CR and 44% PR. The median DoR was 12.2 months (range 0+ to 22.6 months). The median TTR was 1.7 months (range 1.3 to 9.7 months). Safety data were collected in 168 adults with FL and other hematologic malignancies treated with copanlisib. Serious adverse reactions were reported in 44 (26%) patients. The most frequent serious adverse reactions that occurred were pneumonia (8%), pneumonitis (5%), and hyperglycemia (5%). The most common adverse reactions ($\geq 20\%$) were hyperglycemia, diarrhea, decreased general strength and energy, hypertension, leukopenia, neutropenia, nausea, lower respiratory tract infections, and thrombocytopenia. Based on this study, FDA approved copanlisib for the treatment of patients with relapsed FL who have received at least two prior systemic therapies.

In a phase 2, multi-center, open-label trial to evaluate the activity and safety of duvelisib (PI3K α/γ inhibitor) in patients with relapsed/refractory iNHL a total of 129 patients were enrolled, including FL, MZL, and SLL. All enrolled patients were double refractory to rituximab and to either chemotherapy or radioimmunotherapy. The ORR across all indications was 47.3% (42.2% FL, 38.9% MZL). The estimated mDOR was 10 months with an estimated mPFS of 9.5 months. Safety data revealed diarrhea (48.8%), nausea (29.5%), neutropenia (28.7%), fatigue (27.9%), and cough (27.1%) as the most common TEAEs. At least one \geq grade 3 TEAE was experienced in 88.4% of patients, with the most common being neutropenia (24.8%), diarrhea (14.7%), anemia (14.7%), and thrombocytopenia (11.6%) (Flinn 2019).

In a phase 2, multi-center, open-label trial to evaluate the safety and efficacy of umbralisib in previously treated NHL patients, a total of 208 patients were enrolled, including 69 MZL, 117 FL, and 22 SLL. MZL patients were refractory to at least one line of anti-CD20, and FL/SLL patients were refractory to at least two lines of therapy, including an anti-CD20. The ORR in FL patients was 45.3% with 5.1% CR and DoR of 11.1 months (range 8.3-15.6 months). The median TTR was 2.8 months (range 2.7 to 2.9). The ORR in MZL patients was 49.3% with 15.9% CR and DoR not yet reached at time of publication. The median TTR was 2.8 months (range 2.7 – 2.9). Safety data revealed serious adverse events in 28.1% of patients, with 24.6% \geq grade 3. The most common \geq grade 3 AEs were neutropenia (11.5%), diarrhea (10.1%) and increased ALT/AST (7.2%). Other AEs of interest included pneumonitis (all grade 1.4%; \geq grade 3 1.0%), and colitis (all grade 1.4%; \geq grade 3 0.5%) (Zinzani 2020).

Overall, approved PI3k- δ inhibitors have demonstrated a modest ORR in the range of 40% to 50% in FL and MZL. However, they demonstrate a low CR rate of 1-16% and mPFS of less than 12 months. While these agents represent a manageable toxicity profile, high rates of diarrhea, colitis, and hepatic toxicity results in a high rate dose reduction and treatment discontinuation, thereby impacting the long term benefit. Therefore, there is room for a more efficacious and tolerable PI3K- δ inhibitor for treatment of NHL (Dreyling 2017, Zinzani 2020, Flimm 2019).

HMPL-689 is a PI3K δ inhibitor with different molecular structure as compared with idelalisib or duvelisib. Preclinical data shows that HMPL-689 is a small molecule inhibitor with high potency, favorable pharmacokinetic and drug safety profile. The ratio of HMPL-689 biochemical activity in PI3K δ was >100 times stronger than the other PI3K isoforms. Broad kinase selectivity studies demonstrated HMPL-689's high PI3K δ selectivity that is better than idelalisib and duvelisib. Improved isoform selectivity can minimize serious infection that is seen with duvelisib as a result of inhibiting PI3K γ and causing immune suppression. In the ongoing Phase I study (CCI [REDACTED]) out of 18 FL patients ORR of 77.8% (14/18) and CR rate 38.9% (7/18) was achieved as of March 2021. In MZL, 6 out of 12 patients responded (ORR 50.0%). In mantle cell lymphoma, 4 out of 5 patients responded (ORR 80.0%). The evolving clinical data for HMPL-689 from Study CCI [REDACTED] suggests encouraging activity in NHL sub-types such as FL, MZL, MCL and CLL/SLL, with a very tolerable safety profile. High PIK3- δ expression has also been noted consistently in some sub-types of T-cell lymphoma such as peripheral T-cell lymphoma (PTCL) (Huang 2020). Current approved therapies for relapsed/refractory PTCL do not provide consistent efficacy benefit across all sub-types, resulting in a poor overall 5-year survival rate of 10-30% (Coiffier 2014). In phase 1/2 studies, PIK3-inhibitors have demonstrated promising clinical activity with overall responses of ~30% to 50% and an acceptable safety profile (Horwitz 2018, Dreyling 2017), suggesting a role for PIK3-inhibitors such as HMPL-689 in this setting.

Similarly, the paucity of treatment options for relapsed/refractory cutaneous B-cell lymphoma (CBCL) and the potential for PI3K inhibitors to benefit these patients supports the evaluation of HMPL-689 in the study 2018-689-00US1 (Dummer 2012).

Overall, given the importance of the PI3K δ pathway in the lymphomas, HMPL-689's significant efficacy in the preclinical cell lines and preliminary efficacy in lymphoma patients, coupled with its desirable pharmacokinetic and safety profile, HMPL-689 warrants further investigation in clinical studies to fully characterize its potential as a novel small-molecule oral therapy for lymphomas.

3 OBJECTIVES AND ENDPOINTS

Table 1 Objectives and Corresponding Endpoints

Tier	Objectives	Endpoints
Primary – Dose Escalation	To determine MTD and/or RP2D of HMPL-689 in patients with relapsed, refractory, or resistant lymphoma	
 • Incidence of DLTs • Safety (including but not limited to TEAEs, treatment-related adverse events [TRAEs], SAEs, treatment-related SAEs [TRSAEs], and lab abnormalities)
Primary – Dose Expansion	To further evaluate safety and tolerability of HMPL-689 at MTD in patients with relapsed, refractory, or resistant lymphoma	
 • Safety, including TEAEs and TRAEs
Secondary	To assess preliminary efficacy of HMPL689 in patients with relapsed, refractory, or resistant lymphoma overall and by lymphoma sub-types as assessed by investigator	
 • ORR • TTR • DoR • CBR • PFS
	To characterize PK parameters of HMPL-689 in patients with relapsed, refractory, or resistant lymphoma at both dose escalation and dose expansion stages	
 • Concentration-time profiles and PK parameters after single dose and at steady state
	To evaluate the effect of HMPL-689 on cardiac repolarization, as detected by changes in electrocardiogram (ECG) QTc intervals	
 • QTc interval and HMPL-689 concentration

Abbreviations: CBR = clinical benefit rate; DLT = dose-limiting toxicity; DoR = duration of response; MTD = maximum tolerated dose; ORR = objective response rate; PD = progressive disease; PFS = progression-free survival; PK = pharmacokinetic; RP2D = recommended phase 2 dose; SAE = serious adverse event; TEAE = treatment-emergent adverse event; TRAE = treatment-related adverse event; TRSAE = treatment-related serious adverse event; TTR = time to response.

4 STUDY DESIGN

4.1 Overall Study Design

This is a phase 1, open-label, multicenter study of HMPL-689 administered orally daily to patients with relapsed, refractory or resistant lymphoma.

This study will consist of a dose escalation stage (Stage 1) and a dose expansion stage (Stage 2). Both Stage 1 and Stage 2 include the following periods: screening period, treatment period, safety follow-up period, and extended PFS follow-up period, if applicable, as defined in [Appendix 1](#).

The study duration is estimated to be approximately 48 months.

4.1.1 Dose Escalation Stage (Stage 1)

Dose escalation will be performed according to an mTPI-2 ([Yang 2015](#)). HMPL-689 dose escalation will be titrated using a modified Fibonacci design allowing dose increments in subsequent dose levels as listed in [Table 2](#). The guidelines used for dose escalation are shown in [Figure 1](#).

Table 2 Proposed Dose Escalation Scheme

Cohort	Dose Level ^a	Route of Administration
-1	2.5 mg QD	Orally, with water
1	5 mg QD	Orally, with water
2	10 mg QD	Orally, with water
3	15 mg QD	Orally, with water
4	20 mg QD	Orally, with water
5	25 mg QD	Orally, with water
6	30 mg QD	Orally, with water
7	35 mg QD	Orally, with water
8	40 mg QD	Orally, with water
9	45 mg QD	Orally, with water
10	50 mg QD	Orally, with water
X ^b	XX ^b	Orally, with water

Abbreviations: PK = pharmacokinetic; QD = once daily; SRC = safety review committee.

^a The actual next dose will be discussed and decided by the investigators and sponsors based on all previous available data.

^b The need for dose escalation beyond 50 mg QD, or other regimens, such as twice daily, will be evaluated and determined by the SRC based on all available cumulative clinical safety, PK, and efficacy data.

Figure 1 mTPI-2 Decision Chart for Selection of Dose

Number of Patients in a Cohort

	1	2	3	4	5	6	7	8	9	10	11	12
0	E	E	E	E	E	E	E	E	E	E	E	E
1	D	D	S	S	E	E	E	E	E	E	E	E
2		D	D	D	D	S	S	S	E	E	E	E
3			DU	DU	D	D	D	D	S	S	S	S
4				DU	DU	DU	D	D	D	D	D	S
5					DU	DU	DU	DU	DU	D	D	D
6						DU	DU	DU	DU	DU	DU	D
7							DU	DU	DU	DU	DU	DU
8								DU	DU	DU	DU	DU
9									DU	DU	DU	DU
10										DU	DU	DU
11											DU	DU
12												DU

DLT = dose limiting toxicity, E = escalate to the next higher dose; S: Stay at the same dose, D = de-escalate to the previous lower dose, DU = de-escalate to the previous lower dose and the current dose will never be used again in the trial.

Target toxicity probability = 30%; epsilon 1 = 0.05; epsilon 2 = 0.05.

The design characteristics of mTPI-2 are as follows:

- The maximum sample size for this stage will be determined by the sponsor and investigators, based on the accumulated data and the mTPI-2 method (Ji 2013). The maximum recommended sample size under mTPI-2 design is $k \times (d + 1)$, where k denotes the cohort size and d denotes the number of doses. In this study, the minimum cohort size is 3.
- The equivalence interval of toxicity probability for MTD is (25%, 35%). This interval is derived based on the following parameters:
 - The target probability of toxicity (p_T) is set to 30%.
 - Both epsilon 1 (ϵ_1) and epsilon 2 (ϵ_2) are set to 0.05.
- This stage will end when any of the following criteria is met:
 - The dose level 1 demonstrates an excessive toxicity, i.e., 3 DLTs are observed out of the first 3 patients at dose level 1.

- The maximum sample size is reached.
- The MTD and/or RP2D are confirmed.

The rules applied in the dose escalation stage are as follows:

- The starting dose is dose level 1: 5 mg QD.
- If a lower dose is needed upon results from dose level 1, dose level -1 will be explored.
- Three patients will be enrolled for the initial cohort (dose level 1).
- At the end of the DLT assessment window for a dose level, the decision on the dose of the next dose level will follow the rule specified in [Figure 1](#), which leads to enrollment of another 3 patients at the next step.
- In the event that the first two patients within a given dose level experience DLT events but the third patient has not yet begun protocol treatment, the third patient should receive a lower dose per the mTPI-2 algorithm.

At the end of Stage 1, the MTD will be determined based on the number of patients treated and the number of experienced DLTs at each dose level.

Stopping rules for individual patients in the dose escalation stage are located in Section [5.8.3.1](#). Stopping rules for dose cohorts or for the study in the dose escalation stage are available in Section [5.8.4.1](#).

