4.1.1.4 Definition of a DLT-Evaluable Patient

For decisions on dose escalation, each dose cohort shall present protocol-required number of DLT-evaluable patients. Any patient is DLT evaluable if he/she meets the following criteria:

A patient is DLT evaluable if he/she:

- has received at least 75% of the assigned dose of study treatment during the DLT assessment window (i.e., Days 1-28);
- or
- has not completed the DLT assessment period due to a DLT.

Patients who are not DLT evaluable in a dose cohort will be replaced to guarantee the protocol-required number of DLT-evaluable patients for each dose cohort.

4.1.1.5 Dosing Beyond Cycle 1

Patients who complete DLT assessment window and are deemed by the investigator to be benefiting from HMPL-689 treatment may continue with HMPL-689 treatment until disease progression, death, intolerable toxicity, at investigator's discretion that the patient can no longer benefit from the study treatment, withdrawal of consent, or the end of study, whichever occurs first. Conversely, if, in the opinion of the attending principal investigator, the patient may receive clinical benefit from a higher dose, then, at the request of the principal investigator and with the approval of the sponsor, the patient may be able to participate in intra-patient dose escalation (Section 4.1.1.1).

During the study treatment period, including the DLT assessment window, patients will not be allowed to make up missed doses.

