7.3.2 Safety Analysis

Safety parameters, including study drug exposure, DLTs, recorded TEAEs, clinical laboratory parameters, vital signs, 12-lead ECG parameters and physical examination findings, will be summarized by dose level across different stages for the FAS.

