17. SAFETY OUTCOMES

All summary results for safety outcomes will be based on the FAS, except DLTs summaries which are based on the DEAS.

Adverse Events (AEs) will be coded using MedDRA version 26.0 or higher. AE and laboratory test results severity will be performed with the National Cancer Institute Common Terminology criteria for adverse events (NCI CTCAE) V5.0.

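### The end-of-Stage-1 MTD is tied to patients treated rather than DLT-evaluable patients, and no section names the set for the posterior estimate, so one replaced patient can change the selected dose

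*Protocol*

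**What the plan says.** - **MTD, counts to be used.** Protocol 4.1.1, matched by the synopsis, on what happens once escalation is complete: "the MTD will be determined based on the number of patients treated and the number of experienced DLTs at each dose level".
- **MTD, estimator.** Protocol 4.1.1.6 selects the dose whose posterior toxicity probability is closest to 30%, using a beta posterior and the pooled adjacent violators algorithm. There is no MTD if every dose exceeds 35%. Neither the analysis set nor the prior is stated.
- **Escalation decisions.** Protocol 4.1.1.4: "For decisions on dose escalation, each dose cohort shall present protocol-required number of DLT-evaluable patients". Patients who are not evaluable are replaced. Protocol 7.1 and SAP 4.2 expect replacement may take enrolment above plan.
- **Analysis sets.** Protocol 7.2 and SAP 6.4 define a set of DLT-evaluable patients, which the SAP calls the DEAS. Protocol 7.2 does not say what it is for.
- **DLT reporting.** Protocol 7.3.2 includes DLTs in a general list ("Safety parameters, including study drug exposure, DLTs, recorded TEAEs, clinical laboratory parameters, vital signs" and further items) to be summarised on the full analysis set (FAS). Its DLT subsection, 7.3.2.1, plans only a listing. SAP 17 puts safety on the FAS "except DLTs summaries which are based on the DEAS", and SAP 17.1 takes the DEAS as denominator for patients with DLTs.

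**The concern.** A patient who is replaced has been treated but has not been observed for DLT as the protocol requires. If that patient stays in the denominator, an unknown outcome is entered as no DLT, and the estimated toxicity at that dose falls.

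Determining the MTD and/or RP2D is the Stage 1 primary objective. The one sentence that says which counts feed the MTD names treated patients. The section with the estimator is silent, and the SAP, which could have settled it, does not cover MTD estimation. An analyst who follows the protocol as written would use a different denominator from the one used for the escalation decisions and the DLT table.

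**Working it through.** **Inputs.** From Figure 1 and its footnote: "Target toxicity probability = 30%; epsilon 1 = 0.05; epsilon 2 = 0.05", so the equivalence interval is 25% to 35%. The chart is indexed by "Number of Patients in a Cohort". From 4.1.1: "In this study, the minimum cohort size is 3", and each decision is one "which leads to enrollment of another 3 patients at the next step", so the evaluable number at a dose is normally 3, 6 or 9. The beta prior is not given. I assume Beta(1,1) and, as an alternative, Beta(0.005, 0.005). The number of non-evaluable patients is not given either; I assume one at a dose level, with no DLT recorded.

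**Step 1: the plan's own figure.** I used a Beta(1,1) prior, sub-intervals of width 0.10 on either side of (0.25, 0.35), and the DU code when P(p > 0.30) exceeds 0.95. The prior and the 0.95 cut-off are assumptions. This reproduces 89 of the 90 cells of Figure 1. The exception is 2 DLTs in 2 patients (chart D, computed DU), and it disappears if the DU rule starts at 3 patients.

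**Step 2: direction of the error.** With prior Beta(a, a), x patients with a DLT and n patients, the posterior mean is (x + a)/(n + 2a). Adding a patient without a DLT raises only the denominator, so the estimate at that dose always falls.

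**Step 3: effect on the selected MTD.** In each row below the estimates already rise with dose, so pooling leaves them unchanged. Distances are from 0.30.

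| Prior | Lower dose | Higher dose | Distances | Selected |
|---|---|---|---|---|
| Beta(1,1), evaluable | 1/6: 2/8 = 0.250 | 2/6: 3/8 = 0.375 | 0.050, 0.075 | lower |
| Beta(1,1), one extra treated | 1/6: 0.250 | 2/7: 3/9 = 0.333 | 0.050, 0.033 | higher |
| Beta(0.005,0.005), evaluable | 1/6: 1.005/6.01 = 0.167 | 3/6: 3.005/6.01 = 0.500 | 0.133, 0.200 | lower |
| Beta(0.005,0.005), one extra treated | 1/6: 0.167 | 3/7: 3.005/7.01 = 0.429 | 0.133, 0.129 | higher |

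The examples depend on the prior: each pair of data sets changes the selection under its own prior and not under the other. In the last row the selected dose is above 35%, but 4.1.1.6 withholds an MTD only when all doses are above it.

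**Step 4: how often.** Take two adjacent doses with 3, 6 or 9 evaluable patients each and no DU result. That gives 3 + 4 + 5 = 12 outcomes per dose, 12 × 12 = 144 data sets, and 2 × 144 = 288 ways to add one patient. The selection changes in 56 of 288 under Beta(1,1) and in 17 of 288 under Beta(0.005, 0.005). Every change is to the higher dose, or from no MTD to an MTD. The counts are unweighted, include data sets that the escalation may never reach, and depend partly on how ties after pooling are broken. They show that the effect is not confined to one example; they are not probabilities.

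**The case against.** The strongest reply is that treated patients is loose shorthand. Section 4.1.1.4 shows what the protocol means by a usable patient, both documents define an evaluable set, and a competent analyst would use it. That is probably the intent, but no sentence applies that set to the MTD estimate, and the sentence that names a count points the other way.

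It is also fair that practical reach is limited. Section 4.1.1.7 lets PK, safety and efficacy findings inform the RP2D and requires agreement of the sponsor and the safety review committee. Enrolment is halted under Amendment 5, so new wording now affects estimation and reporting, not future escalation. Both points stand; they bear on urgency, not on whether the rule is right.

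Three stronger readings are tempting, and the documents do not support them.

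- *A reader might infer that the DLT rate itself has three competing denominators.* SAP 17 and 17.1 settle it on the DEAS. The FAS sentence in Protocol 7.3.2 is general, is followed by a listing only, and is never linked to the MTD.
- *A reader might infer that the FAS across stages dilutes the DLT rate with Stage 2 patients.* DLTs are assessed only in Stage 1, and SAP 7.9 and 8 summarise the stages separately. No planned analysis yields such a rate.
- *A reader might infer that a replaced patient moves a dose across a Figure 1 boundary.* Figure 1 drives escalation, for which 4.1.1.4 already requires evaluable patients. Even if the extra patient were counted there, starting from 3, 6 or 9 patients, no escalate, stay or de-escalate decision changes. Only 4/6 and 5/9 change, from DU to D.

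The protocol sentence could also be read as counting DLT events rather than patients. This is minor, because Protocol 5.8.4.1 and SAP 17.1 count patients.

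**Conclusion.** Wrong as written, for the MTD estimate only. Section 4.1.1 and the synopsis name treated patients, in conflict with the DLT-evaluable convention of 4.1.1.4 and SAP 6.4, and neither 4.1.1.6 nor the SAP resolves the conflict. The error has one direction: it understates toxicity at the dose where a patient was replaced. One such patient is enough to move the selection up a dose level, as with 0.375 becoming 0.333 beside 0.250 under Beta(1,1).

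This rests on an assumed prior, an assumed single non-evaluable patient without a DLT, and illustrative DLT counts. The documents give no Stage 1 results, so whether the actual MTD would differ cannot be told from them. If no patient at any dose was replaced, the two denominators coincide.

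**What to change.** 1. In Protocol 4.1.1 and the synopsis, base the MTD on the number of DLT-evaluable patients and the number of these with at least one DLT at each dose level. This also removes the ambiguity between events and patients.
2. In Protocol 4.1.1.6, or in a SAP note, state that the posterior estimates use the DEAS. State the beta prior in the same place, since the selection depends on it.
3. In Protocol 7.3.2, take DLTs out of the FAS list, or add the DEAS exception, to agree with SAP 17 and 17.1.

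With enrolment halted, a SAP note before database lock would be enough. The cost is wording only. The estimated toxicity rate may come out slightly higher at any dose where a patient was replaced.
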